4.3 Study Design

[figure not shown]
The design of this study is a single-arm, phase Ib/II study. The overview of the study is shown in **Figure 1**. A total of 25 patients will be enrolled in the study. Once the recommended phase II dose of grapiprant in combination with eribulin is determined, the remaining patients will be treated in the phase II portion, which adds 14 ± 2 days window period of grapiprant treatment alone before the main study to evaluate the effect of grapiprant treatment in the tumor microenvironment and urine prostaglandin E2 metabolite. We will perform a correlative study by collecting tumor and urine samples at pre-and post-window periods. We will ensure the safety of grapiprant and eribulin combination by phase Ib part and determine efficacy in the phase II part—the detail of the trial design described in the **statistical analysis plan (7.0)**.

The starting dose of grapiprant will be 300 mg BID daily orally. Eribulin will be intravenously administered on day 1 and day 8 of every cycle (starting at the FDA-approved dose of 1.4 mg/m²). We define one cycle as 21 days. We will continue the treatment until disease progression, discontinuation by severe toxicity, death, and patient withdrawal. If the patients cannot continue the eribulin because of its toxicity, they will stop eribulin but continue grapiprant as a single treatment until progression or discontinuation. If the patients cannot continue the grapiprant because of its toxicity, they will be off treatment. We will follow-up with the patients up to 5 years after off-treament (see section 4.9). The follow-up can be performed in the clinic in MD Anderson Cancer Center. If the patient is unwilling to come to the clinic, the follow-up would be done by phone.

We will perform imaging analysis by PET-computed tomography (CT) or CT/bone scan at baseline, after the 2 cycles of proposed treatment (does not includes window period), then at the end of every 3 cycles. The Quantitative Imaging Analyzing Core (QIAC) in MD Anderson Cancer Center will independently evaluate the treatment response based on the imaging results.

Protocol 2021-0077 PI: [name] **Proprietary Information of MD Anderson**

Co-PI: [name] Date: 11/22/2022

Product: Grapiprant

Protocol 2021-0077 Proprietary Information of MD Anderson

PI: [name] Co-PI: [name] Date: 11/22/2022

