		\A(I) 4	Cycle 2 and beyond				returns for follow up	30-days Safety F/U ^g	Follow-Up h	
Scheduling Window (Days):		Wk 1 ± 3	Wk 2	Wk 3 ± 3	Wk 4 ± 3	Wk 5 ± 3	# 3	± 7	30 days after the last dose	Yearly, up to 5 years after off study
Informed Consent	Х									
Inclusion/Exclusion Criteria	х									
Grapiprant Administration (daily)		Х	Х	Х	Х	Х	Х			
Eribulin Administration		Х	Х		Х	Х				
Physical Exam ^a , PS ^a	Х	Х			Х			Х		
V/S	Х	Х	Х		Х	Х		Х		
Adverse Events a	X	Х			Х			Х	Х	
Pregnancy Test – Urine or Serum β-HCG (for women with childbearing potential) ^j	Х									
Echo or MUGA ^d	Х									
EKG ^d	Х									
CBC (with diff) ^a	X	Х	Х		Х	Х		Х		
CRP b,	x				Х					
Biochemical Profiles, i, a	х	х			Х			x		
CT scan and bone scan, or PET-CT. Breast MRI, mammogram and/or ultrasound per SOC.	х							х		
Research tumor tissue Collection (metastatic site or primary site [if available]) ^e	Х				х					
Research Blood/Urine Collection f	Х				Х					
Survival Status ^h										Х

Product: Grapiprant Protocol 2021-0077 PI: [name] Co-PI: [name] Date: 11/22/2022

- a. Labs, PS and AEs will not be repeated if it was done within 8 (+/-3 days) days before starting treatment on Wk 1. PE at Wk 1 and day 1 of all subsequent cycles per physician discretion as clinically indicated
- b. C-reactive protein (CRP) will be obtained at baseline and at C2D1 (prior to treatment).
- c. As an evaluation of response, imaging analysis will be performed at baseline, after 2 cycles (C3) of proposed treatment (does not include window period), then at the end of every 3 cycles (C6, C9, C12, etc.). The other radiological evaluation may include ultrasound, bone scan, and X-rays, brain MRI, PET/CT, chest wall/breast photos as clinically indicated for a standard of care.
- d. ECHO, MUGA and EKG will be performed at baseline and as clinically indicated thereafter.
- e. Tumor tissue at the metastatic site or primary site (if available, exclude axillar lymph node) will be collected at baseline and C2D1 (prior to treatment). If the patient had both primary and distant metastasis sites, we would collect sample from the primary site only (excluding axillar lymph node). The biopsy will be done by core needle biopsy, but punch biopsy will be considered if the primary site was a superficial disease. CT-guided biopsy or ultrasonography-guided biopsy will be used based on the location of the metastasis site.

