Research tumor tissue Collection (metastatic site or primary site [if available]) ^e	х			х								
Research Blood/Urine Collection f	Х			Х								
Survival Status h												Х

Product: Grapiprant Protocol 2021-0077 PI: [name] Co-PI: [name] Date: 11/22/2022

- a. Labs, PS and AEs will not be repeated if it was done within 8 (+/-3 days) days before starting treatment on C1D1. PE per physician discretion as clinically indicated at C1D1 and day 1 of all subsequent cycles.
- b. C-reactive protein (CRP) will be obtained at baseline and after the window period of proposed treatment.
- c. As an evaluation of response, imaging analysis will be performed at baseline, after 2 cycles (C3) of proposed treatment, then at the end of every 3 cycles (C6, C9,C12 etc). The other radiological evaluation may include ultrasound, bone scan, and X-rays, brain MRI. PET/CT, chest wall/breast photos as clinically indicated for a standard of care
- d. ECHO, MUGA and EKG will be performed at baseline and as clinically indicated thereafter.
- e. Tumor tissue at the metastatic site or primary site (if available, exclude axillar lymph node) will be collected at baseline and after the window peroid (prior to C1D1 treatment). If the patient had both primary and distant metastasis sites, we would collect sample from the primary site only (excluding axillar lymph node). The biopsy will be done by core needle biopsy, but punch biopsy will be considered if the primary site was a superficial disease. CT-guided biopsy or ultrasonography-guided biopsy will be used based on the location of the metastasis site.
- f. Peripheral blood and urine for correlative studies. Approximately 20 ml of blood (one 10 ml EDTA tube and one 10 ml Red top tube for the serum and PBMCs collection) will be drawn at baseline and after window peroid (prior to C1D1 treatment). For the urine sample, we will collect 10 ml of sample in the urinalysis tube. Urine creatinine will be performed centrally at LabCorp from the frozen urine samples which will be shipped to them in batches.
- g. The mandatory Safety Follow-Up should be conducted approximately 30 days after the last dose of the proposed treatment or before initiating a new anti-cancer treatment, whichever comes first. All AEs that occur before the safety follow-up visit should be recorded. Safety follow-up can be done in the clinic or by phone if the patient is unable to come to the clinic for follow up.

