5.2 Biomarker assessments

In the phase Ib and II part, we will perform a correlative study to determine 1) change in the tumor microenvironment after grapiprant treatment by focusing on the immune cell population, PD-1/PD-L1 expression, and ALDH expression in tumor cells. 2) the role of urine prostaglandin E2 metabolite as a biomarker for grapiprant treatment. A description of each assay is described below.

Tumor Samples

Collection

Tumor tissue at the metastatic site or primary site (if available, exclude axillar lymph node) will be collected before therapy and after completing cycle 1 (phase Ib) and window period (phase II). If the patient had both primary and distant metastasis sites, we would collect sample from the primary site only (excluding axillar lymph node). The biopsy will be done by core needle biopsy, but punch biopsy will be considered if the primary site was a superficial disease. CT-guided biopsy or ultrasonography-guided biopsy will be used based on the location of the metastasis site. We will also collect urine and blood samples before therapy and after the completion of the window period. To ensure the obtained tissue samples include the highest possible proportion of tumor content, we will obtain 4 to 6 cores from the most representative lesions. Those tissues will be preserved by the formalin-fixed and paraffin-embedded (FFPE) form. The pre- and post-biopsy are mandatory both in phase Ib and II part (if applicable). Residual sample materials will be archived at the IBC lab and be available after completion of the designated assays. It may be used in the future for the identification of additional predictive markers or to enhance understanding of disease biology. In that case, we will obtain IRB approval before conducting additional assays. If biomarker samples are drawn but the study drug is not administered, samples will be retained.

Evaluation

We will determine the change in the tumor microenvironment that responds to the proposed treatment by multiplex staining. We will evaluate a population of immune cells (CD8+ T cell, CD4+ T-cell, B cell, Treg, Dendritic cell, and Macrophage [M1/M2]). Expression of PD-L1, PD-1, and ALDH1 on tumor and immune cells are also evaluated.

Urine samples

Collection

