In the phase Ib and phase II part, we will collect a urine sample (phase Ib, before and after cycle 1 treatment; phase II before and after window period). Urine collection is mandatory. The sample collection and processing will be as follows:

Protocol 2021-0077 Proprietary Information of MD Anderson PI: [name]

Co-PI: [name] Date: 11/22/2022

A midstream urine sample should be collected in the clinic by having the patient void the first
part into the toilet, then bringing the urine collection cup into the "midstream" to collect the
urine sample.

- The remainder of the urine may be voided directly into the toilet.
- No part of the interior of the collection cup should be touched with the hands or any other part of the body.
- Place urine sample on ice and prepare an aliquot from the urine sample immediately after the collection (no later than 30 minutes post-collection) to avoid any potential degradation.
- Using a pipette, transfer at least 1mL of urine from the Urine collection cup into one (1) 10 mL Urine Transport tube (white cap).
- Immediately place transport tube on ice.
- The urine transport tube should then be transferred from ice to frozen at ultra-low (-70 degrees Celsius +/- 10 degrees Celsius) as soon as possible.
- Urine creatinine will be performed centrally at LabCorp from the frozen urine sample shipped
 to them in batches. Discard the urine collection cup according to site regulations once the
 creatinine aliquot has been obtained.
- Ship one (1) urine transport tube to Labcorp :

ATTN: BioA Sample Management [name]

Blood samples

Collection

We will collect 20 ml of blood before cycle 1 treatment and after completing the window period (both mandatory). The blood sample will be obtained in one 10 ml EDTA tube and one 10 ml Red top tube for preserving serum and PBMCs. In the event a 10 ml EDTA or 10 ml red top is unavailable, the tubes may be substituted per institutional guidelines. The blood samples will be archived for future research related to this study. The future research will be a predictive biomarker investigation which includes comprehensive cytokine/chemokine analysis by serum and multiple immunoassays by PBMCs. Samples will be stored in IBC lab for 10 years, minimum.

Assays

We will investigate the immunological change in the tumor microenvironment to determine the immunomodulatory effect of grapiprant treatment.

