For each exploratory outcome measure (see 6.2, Biomarker Assessments), samples will be acquired pre- and post-treatment. Change associated with treatment will be assessed by t-test and regression models with relation to treatment time, with adjustment for relevant demographic and baseline covariates. A logistic regression model will be used to assess the association between objective response status and change in exploratory outcomes. A proportional hazard model will be used to assess the association between TTP, PFS, and OS with the change in urine prostaglandin E2 metabolite. Additional statistical methods may be used.

The Investigator is responsible for completing an efficacy/safety summary report and submitting it to the IND Office Medical Affairs and Safety Group, for review and approval.

Phase1b:

After the first 3 evaluable patients complete 1 cycle of study treatment, and every 3 patients thereafter. IND Office approval must be obtained, prior to expanding/changing dose levels.

Phase II:

Toxicity summary will be submitted after the first 9 evaluable patients (including the 6 patients treated at MTD), then every 6 evaluable patients complete 1 cycle of treatment.

Efficacy summary:

If the MTD is 300mg, summary will be submitted after 12 evaluable patients (including the 6 patients treated at MTD), complete 24 weeks of treatment and after the 25 evaluable patients complete 24 weeks cycles of treatment.

If the MTD is 200 mg, Summary will be submitted after 11 evaluable patients (including the 6 patients treated at MTD), complete 24 weeks of treatment, and after 25 evaluable patients complete 24 cycles of treatment.

A copy of the safety summary report should be placed in the Investigator's Regulatory Binder under "sponsor correspondence".

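### The biomarker-change analysis does not separate phase Ib samples (after grapiprant plus eribulin) from phase II samples (after grapiprant alone)

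*Combined protocol and SAP*

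**What the plan says.** **Sampling.** Section 5.2 has tumour tissue "collected before therapy and after completing cycle 1 (phase Ib) and window period (phase II". Urine follows the same split: "phase Ib, before and after cycle 1 treatment; phase II before and after window period". The Study Calendar (Section 4.13, footnote e of each part of Table 5) agrees for tumour. Phase Ib tissue "will be collected at baseline and C2D1 (prior to treatment"; phase II tissue is "collected at baseline and after the window peroid (prior to C1D1 treatment".

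**Exposure.** In phase Ib, grapiprant and eribulin start together, with eribulin planned on days 1 and 8 of a 21-day cycle (Sections 4.3 and 7.0). Phase II, according to Section 4.3, "adds 14 ± 2 days window period of grapiprant treatment alone before the main study". The stated purpose of that window is to see what grapiprant does to the tumour microenvironment and to urine prostaglandin E2 metabolite.

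**Interpretation.** Section 5.2 places both phases under one correlative aim and attributes the change to grapiprant. Section 3.5 likewise sets out to show that grapiprant alters the microenvironment.

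**Analysis.** Section 7.0 says "Change associated with treatment will be assessed by t-test and regression models with relation to treatment time", adjusted for demographic and baseline covariates. Change in the exploratory measures also enters a logistic model for response, and change in urine metabolite enters proportional hazards models for TTP, PFS and OS. No phase, regimen or eribulin term is named. By contrast, the same section summarises CBR and ORR both overall and by dose.

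**The concern.** The phase II window is the one part of the trial where grapiprant can be seen without eribulin. A test that adds the phase Ib pairs mixes a grapiprant-alone change with a combination change. If eribulin alters a marker, the average is neither quantity. A significant result could come from chemotherapy and be reported as immunomodulation by grapiprant; a true grapiprant effect could equally be diluted if eribulin acts in the opposite direction. What is at stake is the mechanistic conclusion and the biomarker read-out, not the efficacy decision.

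**Working it through.** **1. Fix the number of pairs.** The biomarker analysis has no stated sample size or power, so the split comes from the phase II design. The 300 mg rule (continue with at least 2/12, promising with at least 5/25) reproduces Table 7:

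- Early stopping at CBR 10%: 0.9^12 + 12 × 0.1 × 0.9^11 = 0.282 + 0.377 = 65.9% (Table 7: 65.9%).
- Claim promising, exact binomial: 8.33% at CBR 10% and 86.35% at CBR 30% (Table 7: 8.3% and 86.4%).

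The splits (phase Ib + phase II), with a pair assumed from every patient, are:

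- 300 mg, full trial: 6 + (6 + 13) = 6 + 19.
- 300 mg, stopped at the first look: 6 + 6.
- 200 mg, three patients treated at 300 mg: (3 + 6) + (5 + 11) = 9 + 16.
- 200 mg, six patients treated at 300 mg: (6 + 6) + (5 + 8) = 12 + 13.

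**2. Bias of the joint mean.** Let g be the grapiprant effect, d the extra shift from eribulin (both in SDs of change) and w the phase Ib share. The mean over both phases estimates g + w × d. Grapiprant alone is g; the combination is g + d. For 0 < w < 1 and d not zero, the mean equals neither. With 6 + 19, w = 6/25 = 0.24.

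**3. False-positive rate.** Assumptions not in the documents: g = 0, d = 1 (range 0.5 to 1.5), SD 1, two-sided 5%. One-sample t-test on change, 100,000 simulated trials per cell:

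| Pairs (Ib + II) | w | Bias at d = 1 | d = 0.5 | d = 1 | d = 1.5 |
|---|---|---|---|---|---|
| 6 + 19 | 0.24 | 0.24 SD | 8.2% | 16.5% | 27.3% |
| 6 + 6 | 0.50 | 0.50 SD | 11.1% | 26.7% | 45.0% |
| 9 + 16 | 0.36 | 0.36 SD | 12.7% | 32.7% | 56.0% |
| 12 + 13 | 0.48 | 0.48 SD | 19.3% | 54.1% | 83.3% |

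Hand check for 6 + 19 at d = 1: the expected sample variance is 1 + 0.24 × 0.76 × 25/24 = 1.19, so the expected t is about 5 × 0.24/√1.19 = 1.10. Against a critical value of 2.064, this gives about P(Z > 0.96) = 17%, in line with the simulation.

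Tested on phase II pairs alone, the rate stays at 5% for every d and every split.

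**4. Regression on treatment time.** On the nominal schedule, time is 21 days in phase Ib and 14 in phase II, so time = 14 + 7 × phase. The time model and a phase-term model are then the same fit. What the model reports depends on where it is read:

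- At day 14 it returns the phase II mean, and the test holds 5%.
- At the average time it returns the joint mean, with bias w × d.
- At day 0 it extrapolates to a bias of −14 × d/7 = −2d.
- The slope is d/7 per day, an eribulin effect labelled as a time effect.

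With visit windows the correlation of time with phase is about 0.9, and the day-14 test rejects in about 5 to 6% of trials at d = 1.

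**The case against.** Section 7.0 never says that the phases are combined, and it leaves room for further methods. A careful analyst might split them unprompted. That stands as a limit on wording: combining is inferred from the single plan, the shared aim and the absence of a phase term. It does not remove the point, because an open allowance for other methods does not prespecify a split.

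A reader might infer that regression on treatment time is useless because time is fully aliased with eribulin. The documents do not support this. The aliasing is exact only on the nominal schedule, since the window is ±2 days and visits carry ±3 days, and the fitted change at day 14 is protected. The valid criticism is narrower: the SAP does not say where the model is read, and its slope could be misread.

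A reader might also infer that the logistic and hazard models are biased. Every patient goes on to the combination, no calculation shows such bias, and the hazard models use only the urine metabolite. A phase term there is a precaution. It is a reasonable one, because phase also differs in eligibility: measurable disease is required only in phase II.

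The objective in Section 2.3 refers to the proposed treatment, so a combination effect may be of interest. But the phase II pairs contain no eribulin, so the joint mean does not estimate that either.

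Finally, biopsies are taken only where disease is safely accessible, so actual tumour pairs may be fewer. The day 8 eribulin dose can be delayed or omitted, so two doses before the phase Ib post-sample is the plan, not a certainty.

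**Conclusion.** The point holds as a failure to separate two sampling schemes. The difference in exposure is a fact of the protocol. The error rates are conditional on an eribulin effect that the documents do not give, and on the assumptions in the check. Under those, a nominal 5% t-test across both phases rejects in 16.5% of trials at 300 mg with full accrual and 26.7% after a futility stop. On the 200 mg paths it rejects in 32.7% or 54.1%. If eribulin leaves a marker unchanged, there is no inflation.

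The inflation belongs to the unadjusted t-test, not to every reading of the regression. The outcomes touched are the exploratory microenvironment markers and the urine metabolite, whose association with response is secondary. Nothing here bears on DLT, on CBR or on the design's operating characteristics, which reproduce.

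**What to change.** In Section 7.0:

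- Make the phase II window pairs the primary analysis set for grapiprant-associated change.
- Report the phase Ib pairs separately, as change after the combination.
- In any model that uses both phases, including the response and urine-metabolite association models, include an explicit phase or regimen term. If treatment time is kept, state the time at which the fitted change is read.

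No sample or visit changes. The cost is precision in the primary biomarker test. The 95% CI half-width is t/√n in SD units:

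- All 25 pairs: 2.064/√25 = 0.41.
- 19 pairs (300 mg, 6 lost): 2.101/√19 = 0.48.
- 16 pairs (200 mg, 9 lost): 2.131/√16 = 0.53.
- 13 pairs (200 mg, 12 lost): 2.179/√13 = 0.60.

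After a futility stop at 300 mg, 6 of 12 pairs remain and the half-width goes from 0.64 to 1.05. The biomarker result would then be descriptive at best.

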8.0 LABELING, PACKAGING, STORAGE, AND RETURN OF CLINICAL SUPPLIES

8.1 **Investigational Product**

The investigator shall take responsibility for and shall take all steps to maintain appropriate records and ensure appropriate supply, storage, handling, distribution, and usage of investigational product per the protocol and any applicable laws and regulations. Clinical Supplies will be provided by IKENA oncology as summarized in **Table 7**.

Table 8. Product Descriptions

Product Name & Potency	Dosage Form
Grapiprant (100 mg)	Oral Solid Dose Tablet, 50 count bottle

Protocol 2021-0077 Proprietary Information of MD Anderson PI: [name]

Co-PI: [name] Date: 11/22/2022

8.2 Packaging and Labeling Information

Clinical supplies will be affixed with a clinical label per regulatory requirements.

8.3 Clinical Supplies Disclosure

This trial is an open-label; therefore, the subject, the trial site personnel, the designee are not blinded to treatment. Drug identity (name, strength) is included in the label text; random code/disclosure envelopes or lists are not provided.

8.4 Storage and Handling Requirements

Clinical supplies must be stored in a secure, limited-access location under the storage conditions specified on the label. An authorized person must record receipt and dispensing of trial medication at the trial site. Clinical supplies may not be used for any purpose other than that stated in the protocol.

8.5 Returns and Reconciliation

The investigator is responsible for keeping accurate records of the clinical supplies received from IKENA oncology or designee, the amount dispensed to and returned by the subjects, and the amount remaining at the conclusion of the trial. Upon completion or termination of the study, all unused and/or partially used investigational products will be destroyed at the site per institutional policy. The Investigator's responsibility is to arrange for disposal of all empty containers, provided that procedures for proper disposal have been established according to applicable federal, state, local and institutional guidelines and procedures, and provided that appropriate records of disposal are kept.

